5 STUDY EVALUATIONS AND MEASUREMENTS

5.1 Screening and Monitoring Evaluations and Measurements

5.1.1 Initial Screening Interview

See section 3.1.1 for a full description of the initial screening.

5.1.2 ASD/ADHD Diagnosis Verification

To confirm certain inclusion criteria, during the first visit the parent/guardian will be required to present the study team member with a note from a licensed medical professional indicating the subject has been diagnosed with ASD and also if the subject has been diagnosed with ADHD. The study team member will inspect the note, but will not take possession of it.

5.1.3 Medication List

During the initial screening, the parent/guardian will be asked for a list of the subject's medications in the initial screening in order to determine the medication's possible impact on the therapeutic outcomes and research outcomes.

5.1.4 Video Game Interview Form (Parent-Report)

Parents or teachers or therapists will complete a weekly survey on the laptop provided by the Sponsor. The survey will ask questions concerning the subject's enjoyment and progress with the training as well as administration in the home or school environment. Survey is fully described in section 5.4.2.

5.2 Efficacy Evaluations

5.2.1 Primary Endpoints

Please see the primary endpoints listed on page 3-4.

5.2.2 Secondary Endpoints

Please see the secondary endpoints listed on page 3-4.

5.3 Biosensor Data Collection

- *Eye Tracking*: Study participants will be positioned so measurements can be obtained using an eye tracking device available for purchase by consumers Tobii Eye Tracker 4C, or another device of a similar nature. This device uses a camera to measure eye positions and gaze direction to trace where study participants are focused (point of gaze) as they look at stimuli presented on a screen. The device may also measure pupil dilation.
- *Behavior*: Recorded behavioral measures may include computer mouse click, computer keyboard/touchscreen keystroke, touchscreen contact, and game controller game play data.

5.4 Subject and Parent Interviews

5.4.1 Subject Interviews/Surveys

At each study visit and at other times during the course of the study, the subject will participate in brief interviews and/or surveys (which may be conducted in-person or by phone by any member of the study team) including questions about their enjoyment of BioStream Training or alternate game. These interviews will provide an opportunity for subjects to share feedback about BioStream Training with the study team and compare that feedback to feedback regarding the alternate game. All interviews and surveys will be configured (if computer based) so as to include only de-identified subject data. If the surveys are in paper form, the study team member conducting the surveys will only record data in such a manner so that it is de-identified. All such paper based surveys may be converted to digital format (including by use of a scanner) and transmitted to the Sponsor. Additionally, the subject may be asked to complete a brief survey about BioStream Training and/or the alternate game on the Subject Computer which may be transmitted to the Sponsor as described in Section 1.2 Data Transfer and Storage.

5.4.2 Parent/Teacher/Therapist Interviews/Surveys and Equipment Handoff/Return

At each study visit and at other times during the course of the study, the parent/guardian (in the case of the at-home subjects) or teacher or therapist (in the case of in-school subjects or in-center subjects) will participate in brief interviews and/or surveys (which may be conducted in-person or by phone) including questions about the subject's enjoyment of BioStream Training or alternate game. These interviews will provide an opportunity for parents/guardians or teachers or therapists (as applicable) to share feedback about BioStream Training and/or alternate game with the study team. All interviews and surveys will be configured (if computer based) so as to include only de-identified subject data. If the surveys are in paper form, study team member conducting the surveys will only record data in such a manner so that it is de-identified. All such paper based surveys may be converted to digital format (including by use of a scanner) and transmitted to the Sponsor. Additionally, the parent/guardian or teacher or therapist (as applicable) may be asked to complete a brief survey about BioStream Training, the alternate game, and/or provide observational

information regarding the subject (including in the form of a Weekly Parental/Teacher/Therapist survey), on the Subject Computer which may be transmitted to the Sponsor as described in Section 1.2 Data Transfer and Storage. The interviews and surveys will provide an opportunity for parents/guardians or teachers or therapists (as applicable) to share feedback about the at-home, in-school, or in-center administration process (as applicable) with the study team.

Additionally, the parent/guardian or teacher or therapist (as applicable) will be provided with at-home or in-school or in-center equipment (such as a laptop, an eye tracker, such as the Tobii Eye Tracker 4C, and a game controller, such as an Xbox 360 Controller), as well as instructions regarding at-home or in-school or in-center administration of BioStream Training or alternate game. The parent/guardian or teacher or therapist (as applicable) will return the equipment to the study team at the appropriate in-person visit.

STATISTICAL CONSIDERATIONS

5.5 Primary Endpoint

Paired-sample t-tests will be used to measure changes from baseline within each group, and independent sample t-tests will be used to measure changes from baseline relative to the alternate game group for all endpoints.

For all endpoints, we will determine whether there were statistically significant changes in scores from baseline or relative to the alternate game group. Significance will be set at $p < 0.05$. Multiplicity of primary endpoints will be managed via statistical corrections.

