| Study Phases | 
Phase I
 
 • Initial Screening • Visit 1 – Informed Consent, Ekman 60 Faces Test, PPVT • Visit 2 – Assessments and Surveys (Baseline) • Week 1 (following Visit 2) – Gameplay – daily transmission of game data • Week 1 – Survey – data transmission • Visit 3 – Assessments and Surveys • Week 2 – Gameplay – daily transmission of game data • Week 2 – Survey – data transmission • Visit 4 – Assessments and Surveys • Week 3 – Gameplay – daily transmission of game data • Week 3 – Survey – data transmission • Visit 5 – Assessments and Surveys • Week 4 – Gameplay – daily transmission of game data • Week 4 – Survey – data transmission • Visit 6 – Assessments and Surveys 
(Note: Phase II may not begin immediately following phase I)
 
Phase II
 
 • Week 1 – Gameplay – daily transmission of game data • Week 1 – Survey – data transmission • Visit 1 – Assessments and Surveys |

| | |
|--------------------------------------|--|
| | 
 • Week 2 – Gameplay – daily transmission of game data • Week 2 – Survey – data transmission • Visit 2 – Assessments and Surveys • Week 3 – Gameplay – daily transmission of game data • Week 3 – Survey – data transmission • Visit 3 – Assessments and Surveys • Week 4 – Gameplay– daily transmission of game data • Week 4 – Survey – data transmission • Visit 4 – Assessments and Surveys |
| Efficacy Evaluations | 
The primary efficacy endpoints will be:
 
The mean change from baseline score on the following assessments based on post-final game play session assessment compared to the alternate game group:
 
 a. Subject gaze patterns as measured by video eye tracking assessment. b. Subject gaze patterns as measured by the dyadic interaction task. c. Mean change in baseline score on the Ekman 60 Faces Test. d. Mean change in baseline score on the TOVA. e. Mean change in baseline score on the SRS. 
Secondary endpoints:
 
The mean change from baseline score on the following assessments based on post-final game play session assessment compared to the alternate game group:
 
 a. Subject gaze patterns as measured on the videos of emotional expression assessment. b. Subject responses to the CJARS survey. |
| Pharmacokinetic Evaluations | N/A |

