3.4 Study Population

3.4.1 Inclusion Criteria

- 1) Parental/guardian permission (informed consent) and if appropriate, child assent.
 - 2) The parent who participates in the screening, completes the questionnaires, and provides informed consent must be proficient in English.
 - 3) Age 4 years 0 months up to 14 years, 11 months, and 29 days.
 - 4) English as the child's primary/first language (the intervention does not currently have alternate language versions).
 - 5) Capable of using a handheld video game controller (as reported by parent).
 - 6) Has successfully played a video game using a Microsoft Xbox game controller, Sony PlayStation game controller, or other comparable game controller.
 - 7) Parent reports AT LEAST ONE of the following:
 - a) Score of ≤ 2 on a modified version of Question 15 of the Social Responsiveness Scale (SRS) ("Is able to understand the meaning of other people's facial expressions.")
 - b) Score of ≥ 2 on a modified version of Question 16 of the Social Responsiveness Scale (SRS) ("Avoids eye contact.")
 - 8) Confirmed diagnosis of ASD from a licensed medical professional.
-

- 9) Estimated intelligence standard score of at least 40 (can be substituted for a receptive language score such as PPVT or use of the Differential Ability Scales, 2nd Edition (DAS-II)).
- 10) Attains a score equal to or less than 75% correct on the Ekman 60 Faces Test.

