5.6 Secondary Endpoints

See statistical analysis for primary endpoints listed above.

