5.7.2 Efficacy Analysis

The primary analysis will be based on all subjects randomized at the initial visit for who initial visit and final visit data is collected.

Paired-sample t-tests will be used to measure changes from baseline within each group, and independent sample t-tests will be used to measure changes from baseline relative to the alternate game group for all endpoints.

For all endpoints, we will determine whether there were statistically significant changes in scores from baseline or relative to the alternate game group. Significance will be set at $p < 0.05$. Multiplicity of primary endpoints will be managed via statistical corrections.

Secondary endpoints will be evaluated in a similar manner. Analysis will include all subjects for who initial visit and final visit data is collected. The treatment and control groups will be compared using t-tests as described above.

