5.8 Sample Size

This study will enroll up to 150 participants (see section 3.3.1 for details in enrollment timeline).

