 - [34] L. Hoffman, J. Templin, and M. L. Rice, "Linking outcomes from peabody picture vocabulary test forms using item response models," *J Speech Lang Hear Res*, vol. 55, no. 3, pp. 754-63, Jun 2012.
-

ClinicalTrials.gov
Document Submission Cover Page

Official Title of Study: Computer-based Social Skills Training for Autism Spectrum Disorder

NCT Number of Study: NCT03672344

Unique Protocol ID: 08012018A

Document Title: Supplement to Statistical Analysis Plan

Document Date: April 25, 2022

Study Sponsor: BioStream Technologies, LLC

Supplement to Statistical Analysis Plan

In addition to the statistical analyses described in the original study protocol, a 2 (Time) × 2 (Condition) mixed ANOVA was conducted to test for between-group differences in Ekman-60 scores from pre- to post-intervention. Mixed ANOVAs also will be used to test for between-group differences in Social Responsiveness Scale (SRS) and Child Joint Attention Rating Scale (C-JARS) scores from pre- to post-intervention. Significance will be set at $p < 0.05$.

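### Every between-arm test is an unadjusted change-score comparison, so the Visit 2 baseline is never a covariate and precision is usually lost

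*Combined protocol and SAP*

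**What the plan says.** Section 5.5 sets the between-arm comparison for the primary endpoints: "independent sample t-tests will be used to measure changes from baseline relative to the alternate game group for all endpoints". The statistical entry in the Synopsis says the same. For the secondary endpoints, section 5.6 says only "See statistical analysis for primary endpoints listed above", and section 5.7.2 confirms it: "The treatment and control groups will be compared using t-tests as described above". Apart from forming the change score, baseline data have one stated use, the descriptive summaries in section 5.7.1.

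The Supplement to Statistical Analysis Plan (April 25, 2022) reports that a 2 (Time) × 2 (Condition) "mixed ANOVA was conducted to test for between-group differences in Ekman-60 scores from pre- to post-intervention". It plans mixed ANOVAs for SRS and C-JARS in the future tense. It names no covariate. The two gaze primaries, TOVA and the emotional-expression gaze endpoint are not in the supplement and have only the t-test.

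The Synopsis marks Phase I Visit 2 as baseline, and Table 2 schedules every endpoint measure at that visit.

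**The concern.** A change-score test assumes that each extra baseline point carries through to one extra point at the end. The actual slope is b = r × (final SD / baseline SD). If b is not 1, two things follow. A chance baseline difference d between arms moves the estimated effect by −(1 − b)d, and the estimate is noisier than it needs to be.

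Precision matters in this trial. Section 5.8 gives a ceiling ("This study will enroll up to 150 participants") with no power calculation, five primary endpoints share the error rate through unspecified corrections, and the analysis set is limited to subjects with both initial and final data. The supplement may also look like a second, stronger analysis of three endpoints when it repeats the first.

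**Working it through.** **Inputs.** From the documents: t-test on change, two-time-point mixed ANOVA, significance at 0.05, five primary endpoints, at most 150 subjects, random assignment to two groups. Assumed, because the documents are silent: 1:1 allocation, all 150 enrolled and completing (75 per arm), two-sided tests, Bonferroni (0.05/5 = 0.01), r from 0.3 to 0.9, and k = final SD / baseline SD of 0.8, 1 or 1.25. The plan states no power or detectable effect, so there is no figure of its own to reproduce.

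**Step 1: is the mixed ANOVA a different test?** Let D be the between-arm difference in mean change and s² the pooled variance of change. With two time points the interaction sum of squares is D²/[2(1/n₁ + 1/n₂)] and the error mean square is s²/2. Hence F = D²/[s²(1/n₁ + 1/n₂)] = t². On simulated data, t² and F were both 2.9973 (p = 0.0855) with arms of 75 and 75, and both 0.2592 (p = 0.6116) with arms of 70 and 55. ANCOVA on the same data gave different values, 2.860 and 0.551. The identity is with the pooled-variance t-test; a Welch test would differ slightly.

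**Step 2: variance.** In units of the baseline variance:

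- change score: 1 + k² − 2rk
- ANCOVA: k²(1 − r²)
- difference: 1 − 2rk + r²k² = (1 − rk)² = (1 − b)²

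The difference is never negative and is zero only when b = 1. The proportional saving is 1 − k²(1 − r²)/(1 + k² − 2rk), which reduces to (1 − r)/2 at k = 1. At r = 0.5, k = 1: 1 − 0.75/1 = 25%, so 150 subjects act like 150/0.75 = 200. At r = 0.8, k = 1.25: 1 − 0.5625/0.5625 = 0.

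**Step 3: detectable effect.** At 80% power, alpha 0.01 and 75 per arm, the noncentral t gives 0.56 SDs of change. In raw-score SDs at k = 1, multiply by √(2(1 − r)) for the change score and by √(1 − r²) for ANCOVA.

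| r | Saving, k = 0.8 | Saving, k = 1 | Saving, k = 1.25 | 150 act like (k = 1) | Detectable effect, change vs ANCOVA (k = 1) |
|---|---|---|---|---|---|
| 0.3 | 50% | 35% | 22% | 231 | 0.67 vs 0.54 |
| 0.5 | 43% | 25% | 11% | 200 | 0.56 vs 0.49 |
| 0.7 | 37% | 15% | 2% | 176 | 0.44 vs 0.40 |
| 0.8 | 36% | 10% | 0% | 167 | 0.36 vs 0.34 |
| 0.9 | 39% | 5% | 5% | 158 | 0.25 vs 0.25 |

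**Step 4: power for a true difference of 0.4 SD** (alpha 0.05, k = 1, 75 per arm). Change score against ANCOVA: 68.8% vs 80.7% at r = 0.5, 88.5% vs 92.9% at r = 0.7, 97.2% vs 98.3% at r = 0.8. Simulation with 4,000 trials at each r gave 68.0% vs 80.6%, 88.0% vs 92.7% and 96.8% vs 98.2%. Type I error was close to 5% for both methods.

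**Step 5: chance imbalance.** At 75 per arm, 1.96 standard errors of the baseline difference is 1.96 × √(2/75) = 0.32 SD. Multiplying by (1 − r) at k = 1, the change-score estimate shifts by 0.16 SD at r = 0.5, 0.06 SD at r = 0.8 and 0.03 SD at r = 0.9.

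**Step 6: worst case for ANCOVA.** At r = 0.8, k = 1.25, where the formula saving is zero, 40,000 simulated trials gave −0.6%. That is the cost of estimating one slope.

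**The case against.** The strongest reply is that nothing here is wrong. The endpoints are defined as mean change, the t-test tests exactly that, and no power claim in the plan is undermined. The gain runs from nothing to half the variance, and no figure in the documents places any endpoint on that range. That is right as far as it goes, and it is why this is an efficiency point and not a validity error.

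The second reply is about timing. Section 3.3.1 expected completion by February 2020, and the supplement dates from April 2022. Replacing a pre-specified test so late trades pre-specification for an unknown gain. This has force for Ekman-60, whose ANOVA had already been run, and for any other endpoint whose between-arm result had been seen. It has less force for SRS and C-JARS, for which the supplement describes its ANOVAs as still to come.

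Three smaller points stand as caveats. Randomisation guarantees unbiasedness for all randomised subjects, not for the completers who form the analysis set. The ANOVA identity covers three of the seven endpoints. The dyadic, eye-tracking and TOVA endpoints have no single named score; that hinders the planned t-test as much as an ANCOVA.

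**Conclusion.** The concern holds. No between-arm analysis in the protocol or the supplement adjusts for baseline beyond subtraction, and the added ANOVA repeats the pooled t-test. In large samples with 1:1 allocation ANCOVA is never less precise. It is more precise unless the slope of final on baseline score equals 1.

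With equal SDs the gain is worthwhile at low or moderate r (25% of variance at 0.5) and small at high r (5% at 0.9). Unequal SDs can enlarge it or remove it. The variance ratios do not depend on sample size. The detectable effects, power and imbalance figures rest on 75 completers per arm, and the detectable effects also on Bonferroni. The change should be made, but the planned tests remain valid without it.

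**What to change.** In the Synopsis and sections 5.5 and 5.7.2, make the between-arm analysis of each primary and secondary endpoint an ANCOVA. The outcome is the final score at the visit used for the change score; the covariates are arm and the Visit 2 score of the same measure. Name Visit 2 explicitly, because section 5.7.2 refers to the initial visit and Ekman-60 is given at both Visit 1 and Visit 2. Make the same change for SRS and C-JARS in the supplement. Keep the change-score t-tests as a sensitivity analysis.

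Age may be added as a pre-specified covariate. PPVT and site are optional. Their further gain is not quantified, ten sites use up to nine degrees of freedom, and PPVT may not be available for everyone because inclusion criterion 9 allows alternative measures ("can be substituted for a receptive language score such as PPVT").

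Label any ANCOVA of Ekman-60 as post hoc. For every other endpoint, state whether a between-arm result had been seen when the model was changed; where it had, the same label applies.

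The cost is some SAP wording and a few lines of code, since the baseline scores are already scheduled. The real cost is timing: at this date the change cannot count as pre-specified for Ekman-60.

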5.6 Secondary Endpoints

See statistical analysis for primary endpoints listed above.

5.7 Statistical Methods

5.7.1 Baseline Data

Baseline and demographic characteristics will be summarized by standard descriptive summaries (e.g. means and standard deviations for continuous variables such as age and percentages for categorical variables such as gender).

5.7.2 Efficacy Analysis

The primary analysis will be based on all subjects randomized at the initial visit for who initial visit and final visit data is collected.

Paired-sample t-tests will be used to measure changes from baseline within each group, and independent sample t-tests will be used to measure changes from baseline relative to the alternate game group for all endpoints.

For all endpoints, we will determine whether there were statistically significant changes in scores from baseline or relative to the alternate game group. Significance will be set at $p < 0.05$. Multiplicity of primary endpoints will be managed via statistical corrections.

Secondary endpoints will be evaluated in a similar manner. Analysis will include all subjects for who initial visit and final visit data is collected. The treatment and control groups will be compared using t-tests as described above.

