All written or electronic forms (except Informed Consent Forms and Assent Forms) will employ a unique alphanumeric identifier; in no case will the participant's name or other identifying information appear on these forms. The user ID for the BioStream Training and alternate game shall use the same unique alphanumeric identifier. The study team will accomplish this on all parent/guardian or teacher or therapist questionnaires (as applicable) which have lines for child and parent name by applying a label with unique alphanumeric identifier and instructing parents/guardians or teacher or therapists to use generic labels (e.g., biological mother) rather than writing their names. The PI will keep a master list containing PHI and subject ID number separate from coded data forms, which will be maintained in a locked file drawer, cabinet, or lock box in the PI's office. Only the PI will have access to this location. The master list will be maintained on a separate password-protected computer and be stored in an encrypted password protected file. Video recordings will stored on password-protected and/or encrypted data storage devices including computers, external hard drives, and/or flash drives only accessible by members of the study team.

**TABLE 1: SCHEDULE OF STUDY PROCEDURES
(INITIAL SCREENING)**

| | Estimated time | Parent or subject? |
|---|-----------------------|---------------------------|
| Informed Consent | 15 minutes | Parent |
| Review of Inclusion/Exclusion Criteria (Initial Screening Interview) | 15 minutes | Parent |
| Video Game Interview Form (Parent-Report) | 15 minutes | Parent |

**TABLE 2: PHASE I SCHEDULE OF STUDY PROCEDURES
(HOME, SCHOOL, THERAPY CENTER, OR RESEARCH ORGANIZATION)**

| | Estimated time (total over all visits) | Parent or subject? | Visits applicable (Total 6 Visits) |
|--|---|---------------------------|---|
| Informed Consent/Assent (if applicable) | 30 minutes | Parent and subject | Visit 1 |

| | | | |
|---|----------------------------------|----------------|--|
| Peabody Picture Vocabulary Test (PPVT) | 20 minutes | Subject | Visit 1 |
| Ekman 60 Faces Test | 10 minutes | Subject | Visit 1 |
| SRS (Parent-Report) | 50 minutes | Parent | Visits 2-6 |
| C-JARS (Parent-Report) | 50 minutes | Parent | Visits 2-6 |
| Dyadic Interaction Task | 50 minutes | Subject | Visits 2-6 |
| Eye Tracking Video Assessment | 50 minutes | Subject | Visits 2-6 |
| Ekman 60 Faces Test | 50 minutes | Subject | Visits 2-6 |

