| Emotional Expression Video Assessment | 50 minutes | Subject | Visits 2-6 |
| TOVA | 109 minutes | Subject | Visits 2-6 |
| Game and equipment introduction (if applicable) | 40-60 minutes | Parent | Visit 1 |
| BioStream Training | 6.67-33.33 hours | Subject | Over a period of 28 days following Visit 2 |
| Weekly Parental/Teacher/Therapist Survey | 20 minutes | Parent | 1 survey/per week |
| Subject Interview/Survey (if applicable) | 40 minutes | Subject | Visits 3 - 6 |
| Parent/Teacher/Therapist Interview/Survey (if applicable) | 40 minutes | Parent | Visits 3 - 6 |
| Equipment return (if applicable) | 5 minutes | Parent | Visit 6 |
| TOTAL | 13.48 hours – 41.15 hours | Subject | |
| TOTAL | ~4.25 hours* | Parent | *Excludes time spent for oversight of subject during BioStream Training |

**TABLE 3: PHASE II SCHEDULE OF STUDY PROCEDURES
(HOME, SCHOOL, THERAPY CENTER, OR RESEARCH ORGANIZATION)**

| | Estimated time (total over all visits) | Parent or subject? | Visits applicable (Total 4 Visits) |
|---------------------------------------|---|---------------------------|---|
| SRS (Parent-Report) | 40 minutes | Parent | All Visits |
| C-JARS (Parent-Report) | 40 minutes | Parent | All Visits |
| Dyadic Interaction Task | 40 minutes | Subject | All Visits |
| Eye Tracking Video Assessment | 40 minutes | Subject | All Visits |
| Ekman 60 Faces Test | 40 minutes | Subject | All Visits |
| Emotional Expression Video Assessment | 40 minutes | Subject | All Visits |
| TOVA | 87 minutes | Subject | All Visits |
| BioStream Training | 6.67-33.33 hours | Subject | Over a period of 28 |

| | | | |
|---|----------------------------------|----------------|--|
| | | | days |
| Weekly Parental/Teacher/Therapist Survey | 20 minutes | Parent | 1 survey/per week |
| Subject Interview/Survey (if applicable) | 40 minutes | Subject | All Visits |
| Parent/Teacher/Therapist Interview/Survey (if applicable) | 40 minutes | Parent | All Visits |
| Equipment return (if applicable). | 5 minutes | Parent | Visit 4 |
| TOTAL | 11.45 hours – 38.12 hours | Subject | |
| TOTAL | ~2.5 hours* | Parent | *Excludes time spent for oversight of subject during BioStream Training |

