3.1.4 Alternate Game Group

The alternate game group will undergo an estimated 40-60 minute training session on how to use the alternate game on the first visit. Otherwise, their visits will be exactly the same as the BioStream Training Group. Further details on further assessments conducted during the visits can be found in section 4.2

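### Efficacy is analysed in completers only, with no missing-data method or sensitivity analysis, although every primary measure is also taken at the visits between; 5.7.2 leaves its two visits unspecified

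*Combined protocol and SAP*

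**What the plan says.** **Analysis set and test.** Section 5.7.2 states: "The primary analysis will be based on all subjects randomized at the initial visit for who initial visit and final visit data is collected". The same condition is repeated for secondary endpoints. Change is tested by paired t-tests within each group and by independent-sample t-tests between groups. Under 5.5 and 5.7.2, a significant change of either kind counts as a finding.

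**Schedule.** Table 2 places all five primary measures at Phase I Visits 2 to 6, for example "Ekman 60 Faces Test | 50 minutes | Subject | Visits 2-6" and "TOVA | 109 minutes | Subject | Visits 2-6". Table 3 places them at all four Phase II visits, for example "TOVA | 87 minutes | Subject | All Visits".

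**Which visits.** The Study Phases list in the synopsis labels Phase I Visit 2 as baseline. Visit 1 has only one primary measure, the eligibility Ekman test: "Ekman 60 Faces Test | 10 minutes | Subject | Visit 1". Game training is also placed at Visit 1 ("Game and equipment introduction (if applicable) | 40-60 minutes | Parent | Visit 1"), and 3.1.4 describes a "training session on how to use the alternate game on the first visit". The endpoint definition refers to the assessment after the last game session without naming a phase.

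**Loss to follow-up.** Section 4.3 allows withdrawal at any time, and discontinuation by the investigator for missed visits or non-compliance, among other reasons. Section 4.3.1 asks leavers for a voluntary exit interview and mentions no outcome assessment. No expected dropout rate appears anywhere.

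**Supplement (April 2022).** It adds a Time by Condition mixed ANOVA on pre and post scores. This is reported as done for Ekman and planned for SRS and C-JARS.

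**The concern.** Membership of the analysis set depends on events after randomisation. A child who leaves because the game is frustrating or is not helping disappears from the analysis, together with every score already collected after baseline. If such loss is related to outcome, the remaining children look better than the randomised group did. If it also differs by arm, the treatment comparison is distorted.

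The unspecified visits make this worse. If the final visit is Phase I Visit 6, three of the four post-baseline occasions go unused. If it is Phase II Visit 4, seven of eight go unused, and everyone who completes Phase I only is dropped. Phase II need not follow Phase I directly, so loss between phases is foreseeable.

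**Working it through.** The plan gives no power, effect size, SD or dropout figure, so there is none to reproduce. Everything numerical below is illustrative except the ceiling of 150 subjects and the 0.05 level.

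**1. Initial visit.** Read literally, 5.7.2 ties the initial visit to randomisation, and arm-specific training is at Visit 1. On that reading four of the five primary measures have no initial value. The fifth, Ekman, would be a score already required to be 75% or less for entry, which adds regression to the mean to the within-group change. Visit 2 is therefore the only workable baseline, but 5.7.2 does not say so.

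**2. The mixed ANOVA is not a sensitivity analysis.** With two times and two groups, the interaction is tested on D/√2, where D = post − pre. The factor 1/√2 cancels between the effect and error mean squares, so F = t² for the t-test on D. A numerical check gave F = t² = 4.3299, p = 0.0397 for both. In its standard form the ANOVA also uses only subjects with both scores.

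**3. Direction of bias.** Let R = 1 for completers. In one arm the completers' mean change is off by B = E(D | R=1) − E(D) = Cov(D, R) / P(R=1).
- Between-arm bias is B(active) − B(control). It is zero if the two are equal.
- Paired-test bias is B itself. It is zero only if loss is unrelated to change.

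**4. Illustration.** All of the following is assumed: 75 per arm, no true effect, two-sided 0.05, and five occasions (Visits 2 to 6). Random intercept SD is 1.0, slope SD 0.20 per visit, residual SD 0.5. SD of change = √[(4 × 0.20)² + 2 × 0.5²] = √1.14 = 1.07. The chance of leaving after each of Visits 2 to 5 is logistic in the standardised change observed so far, with the intercept set to reach the target loss. Bias is in SD of change.

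| Loss active/control | Selection (logistic slope) | Between-arm bias | Between-arm type I |
|---|---|---|---|
| 20%/20% | same in both arms (−1.5) | 0.00 | 5% |
| 20%/10% | same in both arms (−1.5) | about 0.07 | about 7% |
| 30%/10% | same in both arms (−1.5) | 0.13 to 0.14 | 11 to 13% |
| 10%/10% | active only (−0.75 to −3.0) | 0.03 to 0.12 | 5 to 11% |
| 30%/10% | active only (−0.75 to −3.0) | 0.12 to 0.30 | 10 to 39% |
| 10%/30% | control only (−1.5) | −0.21 | 21% |

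In the first row the paired within-group test has bias 0.14 SD and about 21% false positives. Ranges cover repeat runs, which differ by about 0.01 SD and up to 2 percentage points.

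**5. What an all-visit model recovers.** When loss depends on observed change, a likelihood model using all visits kept between-arm bias within 0.01 SD and type I error at 3.9 to 5.2%. When loss depends on the unobserved final change (30%/10%, active arm only), completers were off by 0.17 to 0.36 SD and the model still by 0.11 to 0.26.

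**6. Precision under purely random 20% loss.** Completers per arm: 75 × 0.8 = 60. SE ratio: √(75/60) = 1.118. Exact t-test power for 0.5 SD falls from 86.0% to 77.5% at 0.05, and from 67.4% to 54.9% at 0.01 (the level if the unnamed multiplicity correction were Bonferroni over five). Simulated power at 0.05 was 77.1% for the completers t-test, 78.6% with baseline adjustment and 80.6% for the all-visit model. So 1.5 of the 3.5 points gained come from baseline adjustment alone.

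**The case against.** Change from baseline to the end of training is a legitimate target. The weakness lies in estimating it from completers alone, not in the two-point contrast.

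Loss may be small and balanced. Section 1.2 provides for reminders and 7.7.1 for gift cards, and a comparator built from the same game makes similar loss mechanisms plausible. This stands as a reason not to presume serious bias. It is not an assurance, because 1.2 also permits any E-rated game as comparator, and balance does not protect the paired tests.

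The largest figures assume selection in one arm only. That is fair, and it is why the table includes equal-selection rows, where the distortion is much smaller. It is also true that the model leaves most of the bias when loss depends on unobserved outcomes.

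Several stronger readings might be inferred but are not supported:
- That the plan names no baseline at all. The synopsis labels Visit 2; what is missing is the link from 5.7.2. The Visit 1 reading is unlikely to be intended, since it leaves four endpoints uncomputable.
- That the trial's results are biased. Without a dropout rate or reasons for loss, this cannot be said.
- That SRS and C-JARS are still unanalysed because the supplement puts their ANOVAs in the future tense. The supplement adds to the protocol's analyses, so the t-tests may already have been run. By F = t², they would already have given the between-arm answer.

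The opposite inference, that equal loss in the arms costs only precision, also fails because of the paired tests.

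**Conclusion.** The concern holds. The complete-case rule is explicit for primary and secondary endpoints, nothing in either document tests it, and the visits that could inform it are already scheduled. The between-arm test is at risk if outcome-related loss differs by arm in amount or mechanism. The paired tests are at risk from any outcome-related loss.

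Under the assumptions above, between-arm type I error ranges from the nominal 5% (same mechanism and amount) through about 7 to 13% (equal selection, unequal loss) to 39% (strong selection in one arm, 30%/10% loss). The paired test reaches about 21% even in the balanced case. These figures show what could happen, not what did. The point should be fixed, and most of the fix remains possible after follow-up has closed.

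**What to change.** 1. In 5.7.2, state that baseline is Phase I Visit 2, and name the final visit as either Phase I Visit 6 or Phase II Visit 4.
2. Analyse all randomised subjects as assigned, with a likelihood-based repeated-measures model using every scheduled visit up to the named final visit. Multiple imputation using those visits is an acceptable alternative. Take both the arm contrast and the within-group changes from it. Prespecify a simpler covariance as fallback: an unstructured matrix needs 5 × 6 / 2 = 15 parameters for five occasions, but 9 × 10 / 2 = 45 for nine.
3. Keep the completers t-tests as sensitivity analyses. Add a missing-not-at-random analysis by arm, such as a delta-adjusted tipping point. Report loss by arm, visit and reason.
4. In a dated amendment, declare for each endpoint whether any between-arm analysis, including the protocol t-test, has been run or seen. Make the model primary only where none has. For Ekman, and for any other endpoint already analysed (SRS and C-JARS included, if so), keep the prespecified t-test as primary and report the model as post hoc sensitivity. The declaration should cover what was seen as well as what was run: section 1.2 lets the sponsor receive study data throughout, and only the video annotators are described as blinded.

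**Cost.** More analysis work, and a missing-at-random assumption that must be stated and tested. The model reduces but does not remove bias if loss depends on unobserved outcomes. No new instruments or visits are needed. Completion was expected by February 2020 and the supplement is dated April 2022, so the cost is probably analysis time only.
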